 - o Any grade 3 or 4 drug-related laboratory abnormality or electrolyte abnormality,

- not associated with underlying organ pathology that does not require treatment except for electrolyte replacements **does not** require treatment discontinuation.
- o Grade 3 or 4 amylase or lipase abnormalities that are not associated with DM, associated liver or gall bladder inflammation clinical manifestations of pancreatitis and which decrease to ≤ Grade 2 within 1 week of onset **may** resume study treatment when resolved.
- Any grade 2 drug-related uveitis or eye pain or blurred vision that does not respond to topical therapy and does not improve to Grade 1 severity within the re-treatment period OR requires systemic treatment.
 - Participants requiring > two dose delays for the same type of event should go off protocol therapy.
 - Any AE, laboratory abnormality, or intercurrent illness, which, in the judgment of the investigator, presents a substantial clinical risk to the participant with continued study drug dosing.
- Any participants who require additional immune suppressive treatment beyond steroids should go off study treatment.
- In participants with HIV-cHL, any participant who requires consolidative therapy with high dose chemotherapy followed by stem cell transplantation will be permitted to go off study therapy.
- Withdrawal of informed consent (participant's decision to withdraw for any reason).
- General or specific changes in the participant's condition, or any clinical AE, laboratory abnormality or intercurrent illness, which, in the opinion of the investigator, indicate that continued treatment with study therapy is not in the best interest of the participant.
- Termination of the study by sponsor.
- Participants treated with systemic steroids, except for a short course of tapered steroids for grade 3 rash and physiologic replacement doses, should be off study.
 - Participants who have been treated with steroids and who do not have an immunologically based event (e.g., infectious pneumonia rather than lymphocytic pneumonitis) may be restarted on treatment if asymptomatic after 2 weeks off all steroids.
 - o Tumor assessments should continue as per protocol even if dosing is interrupted.

4.8 **Duration of Follow-Up**

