4.9 Criteria for Removal from Treatment

Participants will be removed from study when any of the applicable criteria, including PD, AEs, participant withdrawal, or inability to follow study protocol as listed in Section 4.7.

The reason for study removal and the date the participant was removed must be documented in the Case Report Form.

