4.10 Criteria to Resume Treatment

Restarting applies only to grade 2 events and some grade 3 events (skin rash and thyroiditis). The protocol chairs emphasize stopping treatment and starting steroids earlier to obtain resolution with the possibility for restarting rather than waiting for higher grade events.

For non-autoimmune or non-inflammatory events, participants may resume treatment with study drug when the drug-related AE(s) resolve to Grade ≤ 1 or baseline value, with the following exceptions:

- Participants may resume treatment in the presence of Grade 2 fatigue
- Evaluation to exclude any additional immune-mediated events endocrine, GI, and liver/pancreas function as clinically indicated must be made prior to restarting.
- Non-drug-related toxicity including hepatic, pulmonary toxicity, diarrhea, or colitis, must have resolved to baseline before treatment is resumed.

If the criteria to resume treatment are met, the participant should restart treatment no sooner than the next scheduled time point per protocol. However, if the treatment is delayed past the next scheduled time point per protocol the treatment should resume at the earliest convenient point that is within the six-week delay period.

If treatment is delayed for > 35 days for participants on dose levels 1 or -1, or > 42 days for participants on dose levels 2 or -2 (> 56 days for participants on a steroid taper), the participant must be permanently discontinued from study therapy, except as specified in Section 4.7 (Duration of Therapy).

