4.11.2 For Grade 2 symptoms

Moderate reaction requires therapy or infusion interruption but responds promptly to symptomatic treatment (*e.g.*, antihistamines, non-steroidal anti-inflammatory drugs, narcotics, corticosteroids, bronchodilators, IV fluids); close observation for recurrence and treatment medications may need to be continued for 24-48 hours.

Stop the nivolumab infusion, begin an IV infusion of normal saline, and treat the participant with diphenhydramine 50 mg IV (or equivalent) and/or paracetamol 325 to 1000 mg (acetaminophen); remain at bedside and monitor participant until resolution of symptoms. Corticosteroid or bronchodilator therapy may also be administered as appropriate. If the infusion is interrupted, then restart the infusion at 50% of the original infusion rate when symptoms resolve; if no further complications ensue after 30 minutes, the rate may be increased to 100% of the original infusion rate. Monitor participant closely. If symptoms recur, then no further nivolumab will be administered at that visit. Administer diphenhydramine 50 mg IV and remain at bedside and monitor the participant until resolution of symptoms. The amount of study drug infused must be recorded on the electronic case report form (eCRF). The following prophylactic premedication's are recommended for future infusions: diphenhydramine 50 mg (or equivalent) and acetaminophen or paracetamol 325 to 1000 mg should be administered at least 30 minutes before additional nivolumab administrations. If necessary, corticosteroids (recommended dose: up to 25 mg of IV hydrocortisone or equivalent) may be used.

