5.0 DOSING DELAYS/DOSE MODIFICATIONS

5.1 Dose Modifications for Nivolumab and Nivolumab and Ipilimumab Combination

Participants with an overall response of SD, PR, CR, or unconfirmed PD (refer to Section 9.1 for RECIST Criteria, Section 9.2 for KS response evaluation, and Section 9.3 for the 2017 RECIL Criteria for response evaluation) at the scheduled response visits at week 8 and all subsequent visits day 1 of cycles 6 and 9 will be eligible to continue to receive study drug treatments provided that they also have an ECOG performance status score of ≤ 2 , and did not have a DLT or other safety risk requiring discontinuation of the study drugs, as defined below.

Please refer to Appendix X to the protocol for toxicity management algorithms, which include specific treatment guidelines. Where discrepancies occur between Section 5.1 and Appendix X, use the instructions in Section 5.1. These algorithms should be followed unless there are specific clinical circumstances for which the treating physician indicates variations or alternative treatment are needed.

Generally, we strongly encourage early evaluation, withholding drug, and appropriate treatment as indicated in the management tables and following event specific guidelines.

Table 2: Dose Modification Tables for Nivolumab and Nivolumab and Ipilimumab Combination

All Other Events*	Management/Next Dose for Nivolumab and Combination
≤ Grade 1	No change in dose.
Grade 2	Hold** until ≤ Grade 1 OR baseline. Resume at same dose level.
Grade 3	Hold** until ≤ Grade 1 continue at investigator discretion.
Grade 4	Off protocol therapy.

^{*} Not immunologically mediated (excluding clinically insignificant lab abnormalities, see Section 6.4.1)

Recommended management: As clinically indicated.

All Other Events**	Management/Next Dose for Nivolumab and Combination
≤ Grade 1	No change in dose.
Grade 2	Hold until \leq Grade 1 OR baseline. When resolved \leq Grade 1 and off steroids for at least 1 week, resume at same dose level.
Grade 3	Off protocol therapy (exceptions noted in 5.4). May resume nivolumab monotherapy if resolved to Grade 1 or less (off physiologic

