Skin Rash and Oral Lesions	Management/Next Dose for Nivolumab and Combination
Grade 3	$Hold*$ until \leq Grade 1. Resume at same level at investigator discretion.
Grade 4	Off protocol therapy.

^{*}Participants with purpuric or bullous lesions must be evaluated for vasculitis, Steven-Johnson syndrome, TEN, and autoimmune bullous disease including oral lesions of bullous pemphigus/pemphagoid. Pruritus may occur with or without skin rash and should be treated symptomatically if there is no associated liver or GI toxicity. Note skin rash typically occurs early and may be followed by additional events particularly during steroids tapering.

Recommended management: AE management guidelines (Appendix X).

Liver Function (AST, ALT, Bilirubin)	Management/Next Dose for Nivolumab and Combination
≤ Grade 1	Continue protocol therapy.
Grade 2	Hold until UNL or baseline. Resume at same dose level. Consider steroid treatment if > 7 days.
Grade 3	Discontinue protocol therapy if occurring before cycle 5. Initiate IV or PO steroids. May begin nivolumab monotherapy if returns to grade 1 off steroids by week 8 (no earlier than week 6). Hold protocol therapy if occurring after cycle 5. Initiate IV or PO steroids. If not returned to grade 1 off steroids by 6 weeks from missed dose, then off protocol therapy.
Grade 4	Off protocol therapy. Initiate IV steroids.

Continued treatment of active immune-mediated hepatitis may exacerbate ongoing inflammation. Holding drug to evaluate LFT changes, and early treatment are recommended. LFT changes may occur during steroid tapers from other events and may occur together with other GI events including cholecystitis/pancreatitis.

Recommended management: see Hepatic AE management algorithm (Appendix X).

Renal Toxicity	Management/Next Dose for Nivolumab and Combination
≤ Grade 1	No change in dose.
Grade 2	Hold until \leq Grade 1. Resume at same dose level. Steroid treatment if > 7 days.
Grade 3	Hold until ≤ Grade 1. Resume at same dose level.
Grade 4	Off protocol therapy.
Recommended management: see Renal AE management algorithm (Appendix X).	

Diarrhea/Colitis	Management/Next Dose for Nivolumab and Combination
≤ Grade 1	Hold until Grade 0 (if Grade 1) or baseline^. No change in dose.
Grade 2	Hold until Grade 0 or baseline. Steroid treatment if > 7 days

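### Section 4.7 ends treatment after systemic steroids for immune events that Table 2 in Section 5.1 allows to resume, and no text says which rule governs

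*Combined protocol and SAP*

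**What the plan says.** Section 4.7 (Duration of Therapy) sets out what ends treatment. The steroid bullet is: "Participants treated with systemic steroids, except for a short course of tapered steroids for grade 3 rash and physiologic replacement doses, should be off study". A sub-bullet allows a return after steroids only when the event was not immunologically based, infectious pneumonia being its example. Those participants "may be restarted on treatment if asymptomatic after 2 weeks off all steroids". Section 4.9 adopts the 4.7 list as the grounds for removal, closing with "participant withdrawal, or inability to follow study protocol as listed in Section 4.7".

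Table 2 in Section 5.1 has a block for immunologically mediated events that lack a row of their own. At grade 2 the drug is held. Once the event is at grade 1 or below and the participant is "off steroids for at least 1 week, resume at same dose level". In the liver row, a grade 3 event after cycle 5 is held and steroids are started, with this limit: "If not returned to grade 1 off steroids by 6 weeks from missed dose, then off protocol therapy". A participant who recovers in time therefore continues.

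Section 4.10 favours "starting steroids earlier to obtain resolution with the possibility for restarting", but confines grade 3 restarts to skin rash and thyroiditis. Section 4.4 counts a permanent stop of protocol treatment within 6 weeks of the first dose as a DLT.

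**The concern.** A participant with a residual grade 2 immune-mediated event who is treated with systemic steroids and recovers is taken off under 4.7 and resumes at full dose under 5.1. Sites reading different sections would handle the same case differently, and the planned summary of treatment discontinuations in Section 10.1.2 would mix the two practices.

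The primary objective is also touched. If a stop under 4.7 is regarded as permanent and falls in the 6-week window, 4.4 makes it a DLT; under 5.1 the same recovered event is only a dose delay. DLTs are reviewed centrally by the chairs, the medical monitor and the biostatistician, but that group applies the protocol's rules, and here the rules disagree.

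**Working it through.** The plan gives no figure of its own on this point, so the check is mainly a comparison of text.

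**1. Does any 4.7 exception cover the Table 2 cases?** The exceptions are a short taper for grade 3 rash, physiologic replacement, and a non-immunologic event after two weeks off steroids. A grade 2 immune-mediated event in the residual block meets none of them, nor does a steroid-treated immune-mediated grade 3 liver event after cycle 5. For these two rows the conflict is explicit.

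**2. How far does it extend?** The grade 2 rash, liver and renal rows mention steroids and then resumption, but do not expressly link the two. Other text agrees with 4.7: grade 2 pneumonitis and grade 2 neurologic events needing steroids, colitis needing steroids before cycle 5, and the closing note in 5.1 on participants found not to need steroids for an autoimmune event.

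**3. Is there a tie-break?** The only precedence rule places 5.1 above Appendix X. Sections 4.1, 4.4 and 5.2 point generally to Section 5 for dose modification or management; 4.9 points to 4.7 for removal. None ranks 5.1 against 4.7.

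**4. How much time does 5.1 allow?** The delay limits in 4.5, 4.10 and 5.1 are 35 days for single agent, 42 days for combination, and 56 days on a steroid taper, which 5.1 ties to combination therapy. Table 2 requires at least 7 steroid-free days. Time left to resolve and finish steroids = limit − 7:

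- single agent: 35 − 7 = 28 days
- combination: 42 − 7 = 35 days
- combination on a steroid taper: 56 − 7 = 49 days

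**5. Which events can affect DLT counts?** The window is 6 × 7 = 42 days. With 14-day cycles, cycle 5 day 1 falls 4 × 14 = 56 days after the first dose. Grade 3 liver events after cycle 5 therefore affect continuation only; residual grade 2 events can fall inside the window.

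**6. What would one disputed event do?** Under Section 4.2 a level passes at 1/6 or fewer DLTs and is exceeded at the second. With k undisputed DLTs, 2 − k disputed events change the result: one if k = 1 (1/6 becomes 2/6), two if k = 0.

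**7. Where is a dose decision still open?** Section 2.3.8 reports no DLT in the first three evaluable participants at Stratum 1 level 1, and 2.3.9 reports level 2 as tolerable. The documents do not give the status of Stratum 2.

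**The case against.** The best defence is that the protocol, read as a whole, intends resumption. Section 5.1 presents itself as defining the safety reasons for discontinuation. The longer delay for participants on a steroid taper makes sense only if some of them return. Section 4.7 itself removes participants who need immune suppression beyond steroids, a bullet that would be largely redundant if steroids alone already did so. Section 4.10 urges early steroids so that treatment can restart, and 4.6.3 permits steroids for immune-related events. All of this stands as evidence of intent. It is not a ranking, and the rows that agree with 4.7 prevent intent from settling the matter.

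Three stronger readings are tempting and go too far.

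- A reader might infer that under 4.7 the participant can never resume and that the event is automatically a DLT. But the bullet is worded as a recommendation, whereas the delay rules make permanent discontinuation mandatory. A companion sub-bullet speaks of interrupted dosing, and DLT calls go through central review. The only DLT criterion in 4.4 that mentions steroids concerns grade 3 or 4 events.
- A reader might put a number on the dose-finding effect. With an assumed 10% undisputed DLT rate, the chance that a six-participant level passes is 0.9^6 + 6 × 0.1 × 0.9^5 = 88.6%. An assumed extra 1% of participants with a disputed event gives 0.89^6 + 6 × 0.11 × 0.89^5 = 86.6%; an assumed extra 10% gives 0.8^6 + 6 × 0.2 × 0.8^5 = 65.5%. None of these rates is in the documents, so the spread reflects the assumptions alone.
- A reader might cite Section 4.11.2, where an infusion may restart at the same visit after a grade 2 reaction treated with corticosteroids. Applying 4.7 to one acute dose is strained; this is a drafting gap at most.

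The class is also small. Most organ systems have their own Table 2 rows, and 4.7 separately stops grade 2 uveitis that needs systemic treatment.

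**Conclusion.** The conflict is real and should be resolved. For residual grade 2 immune-mediated events, and for steroid-treated grade 3 liver events after cycle 5, the two sections give opposite instructions with no stated precedence. The certain consequence is for continuation of treatment, in any cohort; follow-up under 4.8 continues either way. The DLT consequence is conditional: the event must fall within 42 days of the first dose, the 4.7 stop must be judged permanent, and a Stratum 2 dose decision must still be open. If those conditions hold, one event can be enough to move a level from acceptable to exceeded, but how often that would happen cannot be derived from the documents.

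**What to change.** Three wording changes:

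1. **Section 4.7, steroid bullet:** state that systemic steroids end treatment except where Table 2 in 5.1, or 4.11.2 for infusion reactions, permits resumption.
2. **Section 4.4:** add that a grade 2 event treated with steroids and meeting the 5.1 resumption criteria is not by itself a permanent stop. The existing grade 3–4 criterion stays unchanged.
3. **Section 4.10:** replace the limit to rash and thyroiditis with a reference to the grade 3 events for which Table 2 permits resumption. Adding only the late liver row would be incomplete, because Table 2 also allows grade 3 restarts for renal, fatigue, fever and endocrine events, and nivolumab monotherapy after residual immune events, early liver events, colitis and nausea/vomiting.

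If the sponsor intends the stricter 4.7 rule, the conflicting Table 2 rows should be changed instead; what matters is that one rule remains. The cost is one bullet, one sentence and one phrase in an amendment, with no added procedures or participants.

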4.9 Criteria for Removal from Treatment

Participants will be removed from study when any of the applicable criteria, including PD, AEs, participant withdrawal, or inability to follow study protocol as listed in Section 4.7.

The reason for study removal and the date the participant was removed must be documented in the Case Report Form.

4.10 Criteria to Resume Treatment

Restarting applies only to grade 2 events and some grade 3 events (skin rash and thyroiditis). The protocol chairs emphasize stopping treatment and starting steroids earlier to obtain resolution with the possibility for restarting rather than waiting for higher grade events.

For non-autoimmune or non-inflammatory events, participants may resume treatment with study drug when the drug-related AE(s) resolve to Grade ≤ 1 or baseline value, with the following exceptions:

- Participants may resume treatment in the presence of Grade 2 fatigue
- Evaluation to exclude any additional immune-mediated events endocrine, GI, and liver/pancreas function as clinically indicated must be made prior to restarting.
- Non-drug-related toxicity including hepatic, pulmonary toxicity, diarrhea, or colitis, must have resolved to baseline before treatment is resumed.

If the criteria to resume treatment are met, the participant should restart treatment no sooner than the next scheduled time point per protocol. However, if the treatment is delayed past the next scheduled time point per protocol the treatment should resume at the earliest convenient point that is within the six-week delay period.

If treatment is delayed for > 35 days for participants on dose levels 1 or -1, or > 42 days for participants on dose levels 2 or -2 (> 56 days for participants on a steroid taper), the participant must be permanently discontinued from study therapy, except as specified in Section 4.7 (Duration of Therapy).

4.11 Treatment of Nivolumab-Related and Ipilimumab Combination Infusion Reactions

Since ipilimumab and nivolumab contain only human immunoglobulin or immunoglobulin protein sequences, these agents are unlikely to be immunogenic and induce infusion or hypersensitivity reactions. However, if such a reaction were to occur, it might manifest with fever, chills, rigors, headache, rash, urticaria, angioedema, pruritus, arthralgia, hypoor hypertension, bronchospasm, or other symptoms.

All Grade 3 or 4 infusion reactions should be reported as a SAE if criteria are met. Infusion reactions should be graded according to NCI CTCAE version 5.0 guidelines.

Treatment recommendations are provided below and may be modified based on local treatment standards and guidelines as medically appropriate:

4.11.1 For Grade 1 symptoms

Mild reaction: infusion interruption not indicated; intervention not indicated.

Remain at bedside and monitor participant until recovery from symptoms. Infusion rate may be slowed. If the infusion is interrupted, then restart the infusion at 50% of the original infusion rate when symptoms resolve; if no further complications ensue after 30 minutes, the rate may be increased to 100% of the original infusion rate. Monitor participant closely.

The following prophylactic premedications are recommended for future infusions: diphenhydramine 50 mg (or equivalent) and/or paracetamol 325 to 1000 mg (acetaminophen) at least 30 minutes before additional nivolumab administrations, slowing infusion rate as above.

4.11.2 For Grade 2 symptoms

Moderate reaction requires therapy or infusion interruption but responds promptly to symptomatic treatment (*e.g.*, antihistamines, non-steroidal anti-inflammatory drugs, narcotics, corticosteroids, bronchodilators, IV fluids); close observation for recurrence and treatment medications may need to be continued for 24-48 hours.

Stop the nivolumab infusion, begin an IV infusion of normal saline, and treat the participant with diphenhydramine 50 mg IV (or equivalent) and/or paracetamol 325 to 1000 mg (acetaminophen); remain at bedside and monitor participant until resolution of symptoms. Corticosteroid or bronchodilator therapy may also be administered as appropriate. If the infusion is interrupted, then restart the infusion at 50% of the original infusion rate when symptoms resolve; if no further complications ensue after 30 minutes, the rate may be increased to 100% of the original infusion rate. Monitor participant closely. If symptoms recur, then no further nivolumab will be administered at that visit. Administer diphenhydramine 50 mg IV and remain at bedside and monitor the participant until resolution of symptoms. The amount of study drug infused must be recorded on the electronic case report form (eCRF). The following prophylactic premedication's are recommended for future infusions: diphenhydramine 50 mg (or equivalent) and acetaminophen or paracetamol 325 to 1000 mg should be administered at least 30 minutes before additional nivolumab administrations. If necessary, corticosteroids (recommended dose: up to 25 mg of IV hydrocortisone or equivalent) may be used.

4.11.3 For Grade 3 or Grade 4 symptoms

Severe reaction, Grade 3 symptoms: prolonged (*i.e.*, not rapidly responsive to symptomatic medication and/or brief interruption of infusion); recurrence of symptoms following initial improvement; hospitalization indicated for other clinical sequelae (*e.g.*, renal impairment, pulmonary infiltrates).

Grade 4 symptoms: life threatening; pressor or ventilatory support indicated.

Immediately discontinue infusion of nivolumab. Begin an IV infusion of normal saline, and treat the participant as follows. Recommend bronchodilators, epinephrine 0.2 to 1 mg of a 1:1,000 solution for subcutaneous administration or 0.1 to 0.25 mg of a 1:10,000 solution injected slowly for IV administration, and/or diphenhydramine 50 mg IV with methylprednisolone 100 mg IV (or equivalent), as needed. Participant should be monitored until the investigator is comfortable that the symptoms will not recur. Nivolumab will be permanently discontinued. Investigators should follow their institutional guidelines for the treatment of anaphylaxis. Remain at bedside and monitor participant until recovery from symptoms. In the case of late-occurring hypersensitivity symptoms (*e.g.*, appearance of a localized or generalized pruritus within 1 week after treatment), symptomatic treatment may be given (*e.g.*, oral antihistamine, or corticosteroids).

